1.5 Derived Data

- Study duration (year) = (visit date of last visit – visit date of baseline visit)/365.25

- Completed patients: patients with ≥ 1734 days study duration

- Treatment duration (year):

For completed patients:

(Date of last visit – Date of baseline visit)/365.25

For not completed patients:

Sum of number of weeks/52, months/12 and years patient has been on drug documented on the last visit

If missing: (Date of last visit – Date of baseline visit)/365.25

Note: Some patients stopped Humira temporally. The periods of not taken Humira are not taken into account for the analysis. These patients will be considered as having taken Humira during the complete study.

- Treatment duration category:

0 to 3 months

> 3 to 6 months

> 6 to 9 months

> 9 to 12 months

> 12 to 18 months

> 18 to 24 months

> 24 to 30 months

> 30 to 36 months

> 36 to 42 months

> 42 to 48 months

> 48 to 54 months

> 54 to 60 months

> 60 months

- For the purpose of the analysis of the evolution of parameters over time, follow-up visits will be classified into time windows, defined upon the number of days between Visit 1 and the date of each subsequent visit (PERIOD = Date of follow-up visit - Date of Visit 1)

- Period = Date of visit – Date of baseline visit

- Month 3 window: $1 \leq \text{period} \leq 137$ days

- Month 6 window: $138 \leq \text{period} \leq 228$ days

- Month 9 window: $229 \leq \text{period} \leq 319$ days

- Month 12 window: $320 \leq \text{period} \leq 456$ days

- Month 18 window: $457 \leq \text{period} \leq 639$ days

- Month 24 window: $640 \leq \text{period} \leq 821$ days

- Month 30 window: $822 \leq \text{period} \leq 1004$ days

- Month 36 window: 1005 <= period <= 1186 days
- Month 42 window: 1187 <= period <= 1368 days
- Month 48 window: 1369 <= period <= 1551 days
- Month 54 window: 1552 <= period <= 1733 days
- Month 60 window: 1734 <= period <= 1916 days

Each visit will be classified in a time window. If the date of the visit is completely missing, it will be assumed that the visit took place on the target day of the window as indicated on top of the follow-up page. If more than one follow-up visit is classified into the same time window, the visit closest to the target day is retained. If within a time window there are two visits at the same distance from the target day, the visit which comes first (e.g. before the target date) is retained. If there are two visits on the same date, the first record is retained.

- BASDAI responder: a relative improvement in BASDAI of $\geq 50\%$
- DAS28 category: <2.6 , ≥ 2.6 and ≤ 3.2 , >3.2
- Serious adverse event = event where at least one criteria of seriousness is present
- An adverse event is considered to start in a certain year if the difference between start date and date of baseline (=AEPER) is in the following windows:
 - Year 1: $0 \leq \text{AEPER} < 365.25$
 - Year 2: $365.25 \leq \text{AEPER} < 730.5$
 - Year 3 $730.5 \leq \text{AEPER} < 1095.75$
 - Year 4: $1095.75 \leq \text{AEPER} < 1461$
 - Year 5: $1461 \leq \text{AEPER} < 1826.25$

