3.1.1 Inclusion Criteria

- Patients with ongoing HUMIRA® (adalimumab) treatment who have been prescribed HUMIRA® (adalimumab) within local reimbursement guidelines.

- Patients must be willing to consent to data being collected and provided to Abbott Laboratories

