5 DETERMINATION OF SAMPLE SIZE

Since the purpose of this study is to assess the long-term treatment safety, and efficacy of patients treated with HUMIRA® (adalimumab), as many of these patients as are willing to participate in this follow-up will be enrolled. As it is an observational study, no inferential statistical techniques will be applied to data.

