5.1.2 Planned Methods of Statistical Analysis

Demographics and Baseline Characteristics

Demographic and baseline variables will be described by summary statistics. For continuous data, n, mean, standard deviation, minimum, 1st quartile, median, 3rd quartile, and maximum will be presented. For categorical data, absolute and relative frequency will be calculated.

Safety Analyses

Adverse events will be analysed by presenting frequency and percentage. Furthermore, adverse events of special interest, e.g. serious adverse events, or adverse events leading to discontinuation of treatment with HUMIRA® (adalimumab), will be listed.

Efficacy Analysis

The efficacy analysis of continuous variables (e.g. joint count) will be done descriptively by presenting summary statistics and confidence intervals.

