2 STATISTICAL ANALYSIS

The analysis of the baseline data and prior anti-TNF treatment will be performed broken down by indication (RA, PsA, AS). Within each indication, baseline data will also be presented broken down by completed/not completed patients. Statistical tests will be performed to compare baseline data for patients completed/not completed the study.

The analysis of treatment duration and the evolution of different parameters over time, will be performed broken down by indication (RA, PsA, AS).

The analysis of adverse events will be performed for all patients together and broken down by indication (RA, PsA, AS):

- Overall
- Per year (up to 5 years)
- By cumulative yearly period (till 5 years)
- Incidence
- Incidence divided by total exposure to treatment (till 5 years).
- Reason for seriousness
- Serious adverse events: number of patients and incidence by system organ class and preferred term
- Non-serious adverse events: number of patients by system organ class and preferred term

If an adverse event has no onset date, the observation date will be taken as onset date. Events that are coded with multiple MedDRA Terms will be counted as separate event.

The percentages in the adverse event table are calculated as follows:

Table	Nominator	Denominator
Number of patients with an adverse event per year.	Number of patients treated in that year with at least one adverse event in that year.	Number of patients treated in that year.
Number of patients with an adverse event per cumulative year	Number of patients with at least one adverse event in that year or before.	Number of patients.
Number of adverse events by total exposure to treatment	Number of adverse events in that year or before.	The sum of the patients' treatment exposure time in that year or before.

The following tables will be presented:

Rheumatoid Arthritis

- 1 Baseline Characteristics– All Patients and Broken Down by Early Termination**
 - 1.1 Age
 - 1.2 Gender
 - 1.3 Disease Duration Before Inclusion
 - 1.4 Anti-TNF use Before Inclusion
 - 1.4.1 Anti-TNF Naïve / Experienced
 - 1.4.2 Types of Anti-TNF use Before Inclusion
 - 1.5 Physician's Assessment of Disease Activity
 - 1.6 Clinical Examination
 - 1.6.1 Joint Assessment (tender joints count, swollen joints count)
 - 1.6.2 Inflammatory Parameters (CRP, ESR)
 - 1.6.3 Physical Function (HAQ %)
 - 1.7 Concomitant Medication
 - 1.7.1 Concomitant Steroids
 - 1.7.2 Concomitant NSAIDs
 - 1.7.3 Concomitant Immunomodulators

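### The SAP gives a day-count completion status but no exit reason or event/censor flag, measures treatment duration by two rules, and plans tests that protocol section 5 excludes

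*SAP*

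**What the plan says.** **Completion.** SAP 1.5: "Completed patients: patients with ≥ 1734 days study duration", where study duration is last visit minus baseline visit. The baseline tables in each indication are headed "All Patients and Broken Down by Early Termination", and the day count is the only definition given for that split. SAP section 2 adds: "Statistical tests will be performed to compare baseline data for patients completed/not completed the study". The results go to table 1.9 for rheumatoid arthritis, psoriatic arthritis and ankylosing spondylitis. No test is named.

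**Treatment duration (tables 2.1.1-2.1.4).** For completers it is last visit minus baseline. For the others it is "Sum of number of weeks/52, months/12 and years patient has been on drug documented on the last visit", with last visit minus baseline if that is missing. Of temporary interruptions the SAP says: "These patients will be considered as having taken Humira during the complete study".

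**Exit in the protocol.** Section 3 requires the reason for permanent drug discontinuation. Section 3.4 requires the reason for withdrawal on the Early Termination form. Section 3.3.7 requires that form from completers as well.

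**Inference in the protocol.** Section 5: "As it is an observational study, no inferential statistical techniques will be applied to data". Section 5.1.2, on continuous efficacy variables: the analysis "will be done descriptively by presenting summary statistics and confidence intervals".

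**The concern.** Long-term use is a stated objective in protocol section 2, and the natural question for a five-year registry is how many patients stay on the drug. The planned variables cannot answer it. A patient lost while still on treatment and a patient who stopped because of failure look the same in the completion split and fall in the same duration categories. If completers and non-completers differ at baseline, the report cannot say whether the difference relates to stopping the drug or to being lost.

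The two duration rules are a second problem. The inclusion criterion begins "Patients with ongoing HUMIRA® (adalimumab) treatment who have been prescribed", so patients may enter with earlier exposure. Recorded time on drug may count it. Baseline to last visit does not.

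Third, the tests would produce p-values in three tables that the protocol's own rule excludes, and the SAP does not acknowledge this.

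**Working it through.** **1. The plan's own figure.** The midpoint between Months 54 and 60 is 57 × 30.4375 = 1734.9 days, truncated to 1734, which is the lower edge of the Month 60 window. In years, T = 1734/365.25 = 4.747 (56.97 months). The cut-off is a visit-window edge and says nothing about drug status.

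**2. What is pooled.** No derivation in SAP 1.5 and no listed table uses the exit reason. Only discontinuations caused by adverse events are shown separately, in the adverse event tables. Losses do occur: SAP 1.4 describes artificial visits entered to close lost patients and drops them from every analysis. Dropping those visits is reasonable, but no loss status is carried forward in their place.

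Two further groups may be misplaced:
- *Late stoppers.* Adverse events are recorded up to 3 months after the last dose. A patient who stopped near day 1734 − 3 × 30.4375 = 1643 and was seen three months later would count as completed.
- *Data cut.* The data were received on 5 February 2018. A patient enrolled after 8 May 2013 (1734 days earlier) could not be completed by then, even if still on drug. The documents give no enrolment end date, so the number is unknown.

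**3. Duration categories.** Day 1826 is 59.99 months. Completers last seen on days 1734-1826 therefore share the category from 54 to 60 months with patients who stopped.

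**4. Time origin (conditional example).** Suppose recorded time runs from the first injection. A patient with 12 months of prior use who stops at Month 54 is recorded at 12 + 54 = 66 months, in the category above 60. A completer with the same prior use, last seen on days 1734-1826, is in the category from 54 to 60. The form field is not in the documents, so whether this happens is unknown.

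**5. Size of pooling losses with stops (illustration, assumed rates).** Let R5 be five-year retention implied by recorded stops, s = −ln(R5)/5, l the yearly loss rate, and p the share of lost patients who had in fact stopped when lost. Rates are constant and independent.
- Share still followed on drug at day 1734 = exp(−(s + l)T)
- True retention at day 1734 = exp(−(s + p·l)T)

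At l = 0.05 per year:

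| R5 | s | Still followed | True, p = 0 | True, p = 0.5 | True, p = 1 | Gap, p = 1 to p = 0 |
|---|---|---|---|---|---|---|
| 30% | 0.2408 | 25.1% | 31.9% | 28.3% | 25.1% | 0 to 6.7 points |
| 50% | 0.1386 | 40.8% | 51.8% | 46.0% | 40.8% | 0 to 10.9 points |
| 70% | 0.0713 | 56.2% | 71.3% | 63.3% | 56.2% | 0 to 15.1 points |

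With p = 0, the upper end over R5 of 30-70% is 2.9-6.5 points at 2% yearly loss and 12.0-26.9 points at 10%. Losses make up l/(s + l) of exits: 0.05/0.2908 = 17% to 0.05/0.1213 = 41% at 5% yearly loss.

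Censoring the losses gives the p = 0 column. Counting them as stops gives the p = 1 column. In this model the two analyses bracket the truth.

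**6. Inference rule.** Protocol section 5 excludes inferential techniques, protocol 5.1.2 plans confidence intervals, and SAP section 2 plans tests. The three cannot all stand without an explanation.

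**The case against.** The strongest reply is that nothing planned is wrong on its own terms. The SAP does derive a binary exit status and uses it. Table 1.8 shows study duration separately for completers and non-completers. The duration tables are titled only as treatment duration, and neither document names retention as an estimand. That stands: the tables are valid descriptions of observed duration, and a retention curve is an addition that serves the long-term-use objective.

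Three stronger readings are tempting, and the documents do not support them.
- *That the SAP has no exit status.* It has one; the reason and the event/censor flag are missing.
- *That the duration tables understate retention.* Loss on drug shortens observed time, but possible pre-enrolment use lengthens it for non-completers, and temporary stops count as time on drug. The net direction is undetermined.
- *That 7-15 points is the bias.* It is the upper end at one assumed loss rate, vanishes if all lost patients had stopped, and describes no quantity in a planned table.

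On the tests, it is fair to say that they are baseline attrition comparisons with no efficacy claim, that the protocol sentence sits in the sample size section, and that 5.1.2 already plans intervals. This softens the conflict without removing it. SAP 1.4 leaves data handling rules to the statistical report, but a rule first written there is not pre-specified.

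**Conclusion.** The point holds in a limited form and should be acted on. Three things follow from the text without assumption: exit reasons are pooled in the baseline comparison and the duration tables; treatment duration follows different rules for completers and non-completers; and the planned tests contradict protocol section 5 without comment, while 5.1.2 is itself not fully in line with that section.

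The numerical effect is unknown because the documents give no loss counts. The illustrative gap between the share still followed on drug and true retention is 0 to about 7-15 points. It assumes constant, independent rates, 5% yearly loss and 30-70% five-year retention, and where it falls in that range depends on how many lost patients had stopped. No direction or size is claimed for tables 2.1.1-2.1.4. The time-origin effect depends on a form field that is not shown.

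**What to change.** 1. Measure treatment duration from the baseline visit in all patients, and label tables 2.1.1-2.1.4 as observed duration.
2. Derive the exit reason from the Early Termination form: drug discontinuation, loss to follow-up, death, other withdrawal, data cut or study end, missing. Split the not-completed group by it.
3. Add Kaplan-Meier retention from enrolment in each indication. The event is permanent discontinuation by recorded reason, whatever the 1734-day status. Date it at the recorded stop date or, if there is none, at the last visit, and state that limit: the cited protocol sections require a reason but not a stop date, and the last visit can fall after the last dose. Censor lost, withdrawn, data-cut and still-on-drug patients at the last visit, and state the non-informative-loss assumption. Assign death and missing reason explicitly. Add a sensitivity curve that counts lost and missing-reason patients as stopped, and show both curves.
4. Make the completed/not-completed comparison descriptive, or document the departure from protocol section 5, name the tests and label them exploratory. In either case, say how the confidence intervals of 5.1.2 fit the rule.

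The cost is SAP wording, one derived variable from reasons the protocol already asks for, work on stop dates, and standard survival code. The curves describe retention from enrolment, not from first injection. If losses are many they may lie far apart, and the report must show that range.

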3 INVESTIGATIONAL PLAN

This is a multi-center, uncontrolled observational study of patients who at the time of entry were prescribed with HUMIRA®(adalimumab) following normal clinical practice, with or without other anti-rheumatic treatments, prior to enrollment in this study.

Patients will be followed for 5 years within the post-marketing observational study.

Physicians will be provided with a study kit that includes a protocol, patient informed consent forms, adverse event report forms, and Data Report Forms (DRFs), for each patient to be enrolled. The participating physician will already have provided a prescription to the patient for HUMIRA®(adalimumab), along with instructions for appropriate use according to the European Union (EU) Summary of Product Characteristics (SPC).

Once the physician has determined that the patient meets the inclusion criteria, and the patient has agreed to be included in the observational study, the patient's baseline demographic data, and disease status will be reported in the Baseline DRF. The physician will then follow-up the patient via regular office visits at intervals as determined by routine clinical practice or as recommended by national guidelines.

Patient's safety and efficacy data if they are part of clinical routine will be recorded in the DRFs at Baseline, and regular visits which are closest to Month 3, Month 6, Month 9, Month 12, Month 18, Month 24, Month 30, Month 36, Month 42, Month 48, Month 54, and Month 60. While the physician will likely deem it appropriate and necessary to have the patient return for intermediate visits during the study period, data will be collected via DRFs only at the intervals which correspond closely to those described above. Physicians are encouraged to treat their patients as they would in their routine clinical practice. If treatment with HUMIRA®(adalimumab) is permanently discontinued for any reason, patients will be discontinued from the study and the reason should be recorded. Physicians will be asked to record adverse events up to 3 months after last administration of HUMIRA®(adalimumab) on the DRF of the next scheduled data collection time.

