3.3.7 Data Report Form (DRF) Completion and Collection

All data associated with this study will be collected and reported via DRFs on 2-part NCR paper or electronically via the web address and password which will be provided. If using paper DRFs the top copy of the form should be forwarded to the data coordination center, the second copy of the form should be retained at site.

At the baseline visit, the investigator should complete the Baseline Data Report Forms by collecting and reporting on the forms all available required information, including visit date, demographic data, concomitant diseases and medication, etc. If using paper DRFs the enrolment fax should be completed and faxed immediately to the data coordination center.

At subsequent visits corresponding to the schedule of assessments (Table 1), the investigator should complete the appropriate DRF by collecting and reporting on the forms all available information. Since this is an observational study, data from the patient visit following normal clinical practice, which most closely corresponds to the recommended schedule of assessment at Month 3, Month 6, Month 9, Month 12, Month 18, Month 24, Month 30, Month 36, Month 42, Month 48, Month 54, and Month 60 will be accepted.

If the subject is withdrawn from the study at any time or completes the 5-year observation period an Early Termination DRF should be completed.

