3.4 Withdrawal of Subjects from Study

A subject may withdraw from the study at any time without prejudice. The investigator may discontinue any subject's participation for any reason. If a patient withdraws or is withdrawn from the study, such should be noted, along with the reason for withdrawal, on the Early Termination DRF.

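### SAP 1.5 counts a patient who stops adalimumab permanently after Month 54 as completed, and as treated to the last visit, if a dated Month 60 form exists

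*SAP*

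**What the plan says.** Protocol section 3 plans a fixed follow-up: "Patients will be followed for 5 years within the post-marketing observational study". It also ties participation to treatment: "If treatment with HUMIRA®(adalimumab) is permanently discontinued for any reason, patients will be discontinued from the study and the reason should be recorded". Physicians are then asked to "record adverse events up to 3 months after last administration of HUMIRA®(adalimumab) on the DRF of the next scheduled data collection time".

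Two protocol sections deal with closing a patient. Section 3.3.7: "If the subject is withdrawn from the study at any time or completes the 5-year observation period an Early Termination DRF should be completed". Section 3.4 has a withdrawal noted "along with the reason for withdrawal, on the Early Termination DRF".

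SAP 1.5 derives study duration as last visit minus baseline visit and then states: "Completed patients: patients with ≥ 1734 days study duration". For completed patients, treatment duration is the same difference, last visit minus baseline. For the others it is the time on drug documented at the last visit, with last visit minus baseline as the fallback if that is missing. The Month 54 window is days 1552 to 1733 and the Month 60 window is days 1734 to 1916.

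SAP section 2 uses the completed flag to split the baseline tables within each indication and to test the two groups against each other. It uses treatment exposure as the denominator of the adverse event rates.

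**The concern.** Under the protocol, a patient who has permanently stopped adalimumab has left the study. The SAP definition has no condition on treatment status or on the reason for termination, although the baseline tables it serves are titled as a split by early termination.

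The protocol itself supplies a route into the wrong group. For a patient who stops after the Month 54 visit, the next scheduled form is Month 60. The window for that form opens on day 1734, the same day as the completion cut. If the form is filled in as asked and carries a visit date, two things follow:

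- The patient moves from not completed to completed.
- The treatment-duration formula switches from documented time on drug to last visit minus baseline, so time after the last dose counts as treatment.

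Both errors run in one direction. They touch the completed/not completed comparison in tables 1.1 to 1.9 and treatment duration in tables 2.1.1 to 2.1.4. Through treatment exposure they also touch the adverse event rates in tables 3.5.

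**Working it through.** **The threshold.** The midpoint of Month 54 and Month 60 is 57 × 365.25/12 = 1734.9 days, which matches the SAP's 1734. In years, 1734/365.25 = 4.75, which is 1826.25 − 1734 = 92 days short of five years. The cut is therefore the opening of the Month 60 window and says nothing about treatment.

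**Effect on one patient.** Overstatement = day of last visit − day of stop.

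- Stop on day 1644 (Month 54 target), form on day 1826: 182 days. The SAP gives 5.00 years; time treated is 4.50 years.
- Stop on day 1735 (Month 57), form on day 1826: 91 days.
- Stop on day 1552, form on day 1916 (outer window limits): 364 days.
- Stop on day 1660, form on day 1830: 170 days. The duration moves from 54.5 to 60.1 months, one category up.

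**How many patients.** The documents give no discontinuation rate. I assume a constant yearly stopping rate h of 5%, 10% or 20%, and a Month 60 form for every such patient. With S(d) = exp(−h × d/365.25), the share affected is S(1644) − S(1734) if the Month 54 visit is on target, or S(1552) − S(1734) if it is on the first day of its window. SAP 1.2 gives n = 5920. Results come from unrounded values.

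| h | S(1552) | S(1644) | S(1734) | Stops from day 1644 | Stops from day 1552 |
|---|---|---|---|---|---|
| 5% | 0.809 | 0.798 | 0.789 | 0.98% (58) | 2.0% (118) |
| 10% | 0.654 | 0.638 | 0.622 | 1.55% (92) | 3.2% (188) |
| 20% | 0.427 | 0.406 | 0.387 | 1.95% (116) | 4.1% (240) |

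**Against sampling error.** The split is made within each indication, so the standard error is √(p(1 − p)/n), with p = S(1734) and n from SAP 1.2. The ratio is the day-1644 share divided by this standard error.

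| Indication (n) | SE in points at h = 5%, 10%, 20% | Ratio |
|---|---|---|
| RA (2836) | 0.77, 0.91, 0.91 | 1.3, 1.7, 2.1 |
| AS (1957) | 0.92, 1.10, 1.10 | 1.1, 1.4, 1.8 |
| PsA (1127) | 1.22, 1.44, 1.45 | 0.8, 1.1, 1.3 |

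Relative to the patients still on drug at day 1734, the completed group is too large by 0.98/78.9 = 1.2% to 1.95/38.7 = 5.1%.

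**Exposure.** With Month 60 forms on day 1826, the mean overstatement for stops on days 1644 to 1733 is about 137 days. Excess exposure is number affected × 137/365.25 = 22, 35 and 44 patient-years. Total exposure is 5920 × (1 − exp(−5h))/h, about 26,200, 23,300 and 18,700 patient-years. The excess is 0.08%, 0.15% and 0.23%. Counting from day 1552 (mean overstatement about 184 days), it is 59, 95 and 121 patient-years, or 0.2% to 0.65%.

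**The case against.** The strongest counter-argument is that the route is inferred. The protocol discontinues a permanent stopper and closes the record with an Early Termination DRF. The sentence about the next form asks for adverse events to be recorded and does not require another office visit. The documents do not show whether such an entry carries a date that counts as the last visit. SAP 1.2 reports corrections for misclassified visits, and SAP 1.4 leaves the data handling rules to the Statistical Report. A cut at the Month 60 window is also a recognisable working definition in a study that relies on routine visits. This stands as a limit on size: the error arises only where a dated form exists. It does not supply the missing condition. The SAP note on interruptions covers temporary stops only. The excluded LT visits are administrative closures of patients lost to follow-up, not forms filed after a stop.

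A reader might infer more than the documents support in four ways:

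- **Pooling all 5920 patients** would give 1.8 to 3.1 standard errors. The SAP makes the completed split only within indication, and its all-patients tables contain adverse events only.
- **Treating 1.0% to 2.0% as a ceiling.** It is not one, because the Month 54 window opens on day 1552. Nor is it an estimate, because it shrinks with every missing Month 60 form.
- **Expecting distorted adverse event rates.** The exposure figures show a change well under 1%.
- **Reading the SAP's completed count as the number on adalimumab at five years.** The SAP never says this; it speaks of completing the study, and no listed table has the completion percentage as its endpoint.

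**Conclusion.** The gap is real. SAP 1.5 as written classes a late permanent stopper with a dated Month 60 form as completed and treated to that visit, which does not fit the protocol's rule on permanent discontinuation. The two texts need to be reconciled.

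The size is modest and conditional. It depends on an assumed constant stopping rate, on complete Month 60 forms and on those forms carrying a visit date. It bears on who sits in which column of the baseline comparison and on the upper duration categories. No effect on any particular baseline test has been shown. The database was already in hand when the SAP was written, so the true number can be counted instead of assumed.

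**What to change.** In SAP 1.5, define completed as at least 1734 days of study duration and no permanent adalimumab discontinuation given as the reason on the Early Termination DRF. The form's presence alone cannot separate the groups, because five-year completers file it too. For every permanent stopper, take treatment duration from the on-drug time documented at the last visit, keeping the existing fallback where it is missing. Report by indication how many patients change group.

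The rule should rest on these fields because the documents do not show that a stop date is recorded. Without a date, it also moves patients who stop after day 1734 and have that reason recorded. This agrees with Protocol section 3 but is not included in the counts above.

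The cost is two sentences in the SAP and one extra condition in the derivation program. The completed count becomes slightly lower, and stoppers with missing on-drug time keep the last-visit duration.

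### Table 3.5 does not define its treatment exposure or limit adverse events to the same time, and the treatment duration tables show lost patients like patients who stopped

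*SAP*

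**What the plan says.** SAP 1.5 derives Treatment duration in two ways. For completers (study duration of at least 1734 days) it is last visit minus baseline visit, in years. For the others it is "Sum of number of weeks/52, months/12 and years patient has been on drug documented on the last visit", and visit dates are used only if that total is missing. On temporary stops the SAP adds: "These patients will be considered as having taken Humira during the complete study".

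SAP 2 sets the numerator of the exposure-based AE table (3.5) as "Number of adverse events in that year or before" and the denominator as the sum over patients of "treatment exposure time in that year or before", up to five years. SAP 1.5 does not define that exposure term. It counts AE years from baseline, with Year 5 ending at day 1826.25. For missing onsets, SAP 2 states: "If an adverse event has no onset date, the observation date will be taken as onset date". The per-year table (3.2) has a narrower numerator: "Number of patients treated in that year with at least one adverse event in that year".

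Protocol 3 asks physicians to record AEs for 3 months after the last administration. Protocol 3.1.1 enrols patients whose treatment is already ongoing. Protocol 3.4 puts the reason for withdrawal on the Early Termination DRF.

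Tables 2.1.1 to 2.1.4 present Treatment duration overall, by category, by year of start and by Month 6 DAS28 category. No censoring is listed. SAP 1.4 drops the closing (LT) visits of lost patients from every analysis and leaves data handling rules to the statistical report.

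**The concern.** Table 3.5 is the only AE output divided by treatment time, and long-term safety is a main aim of the study. A rate needs events and time drawn from the same period. Here the events are dated from baseline and may fall after the last dose. For many non-completers the time may come from an undated total whose start is not given. A programmer would have to choose the variable, the start and the allocation rule, and SAP 1.4 lets that choice appear only in the report.

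The duration tables raise a separate issue. A patient lost while on drug, or still on drug at the last visit, has a duration that is only a lower limit. Summarised beside true stops, it will be read as time to stopping.

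**Working it through.** The plan states no person-year total, loss rate or AE rate, so there is no figure to reproduce. The indication counts do agree: 2836 + 1127 + 1957 = 5920.

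**1. Allocating the total to study years.** Let D be the on-drug total and V the time from baseline to last visit, in years.
- If the clock starts at baseline and gaps count as treated, cumulative exposure by Year k is min(D, k). With D = 1.5 this gives 1.0, 1.5 and 1.5 by Years 1, 2 and 3.
- If the D years may lie anywhere before V, the bounds are max(0, D − (V − min(V, k))) to min(D, k). With D = 1.5 and V = 3.0 they are 0 to 1.0, 0.5 to 1.5, and 1.5.
- If D includes P years before baseline and V = 1.0, allocation from baseline gives 1.25, 1.5, 2.0 and 3.0 years for P = 0.25, 0.5, 1 and 2, against a true 1.0. This lowers the rate.

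D, V and P are illustrative. A split is possible, but the SAP does not state the rule or the start.

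**2. Post-dose AEs, one patient.** Take a last dose on day 340 and an AE on day 380. In table 3.2, if treated means on drug, the patient is not treated in Year 2 and the AE is left out. In table 3.5 the AE counts in the cumulative Year 2 numerator. The 340 days are in the denominator and the 40 days after the last dose are not. If the on-drug total were missing, the denominator would run to the last visit and might include those days, so the mismatch differs between patients. A full 3-month tail is 0.25/0.25 = 100% of exposure for a patient who stopped at 3 months, 0.25/1 = 25% at 1 year and 0.25/4.5 = 5.6% at 4.5 years.

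**3. Post-dose AEs, whole cohort (assumption-based).**
- SAP 1.2 gives 47378 − 5947 = 41431 follow-up records, and 41431/5920 = 7.0 per patient, or 58% of the 12 scheduled visits. The records were counted before cleaning and the patients after it.
- Assume each record is one visit attended in order, and a share c of patients has all 12. Non-completers then have (7.0 − 12c)/(1 − c) visits: 4.85, 3.66 and 2.00 for c = 0.30, 0.40 and 0.50. On the visit schedule that is t = 1.43, 0.92 and 0.50 years.
- Mean follow-up is D̄ = 5c + (1 − c)t = 2.50, 2.55 and 2.75 years.
- Mean tail is T = (1 − c) × s × 0.25, where s is the share of non-completers who stopped drug (0.5 to 0.9). Let k be the share of post-dose AEs captured (0.25 to 1).
- The rate ratio is (D̄ + kT)/D̄. Low (c = 0.50, s = 0.5, k = 0.25): 1 + 0.0156/2.75 = 1.006. Middle (c = 0.40, s = 0.7, k = 0.5): 1 + 0.0525/2.55 = 1.021. High (c = 0.30, s = 0.9, k = 1): 1 + 0.1575/2.50 = 1.063.

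D̄ is time to the last visit. Where that visit falls after the last dose, D̄ already holds part of the tail and the true effect is smaller.

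**4. Raw duration against censored duration (assumption-based).** Assume a constant stop hazard h and an independent loss hazard l per year. The raw share beyond 54 months is exp(−4.5(h + l)), and the censored share is exp(−4.5h). The means to 5 years are (1 − exp(−5(h + l)))/(h + l) and (1 − exp(−5h))/h. With h = 0.15:

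| l | share > 54 months, raw | censored | mean to 5 years, raw | censored |
|---|---|---|---|---|
| 0 | 50.9% | 50.9% | 3.52 | 3.52 |
| 0.05 | 40.7% | 50.9% | 3.16 | 3.52 |
| 0.10 | 32.5% | 50.9% | 2.85 | 3.52 |
| 0.15 | 25.9% | 50.9% | 2.59 | 3.52 |

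Over h = 0.10 to 0.20 and l = 0.05 to 0.15, the raw share is 8 to 31 percentage points too low as an estimate of retention. With no loss there is no gap. Steps 3 and 4 use separate assumptions and should not be combined.

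**The case against.** The strongest reply is that this is mostly a wording gap. Treatment duration is the evident candidate for the denominator, the five-year limit is stated, and counting interruptions as treated is disclosed. The duration tables claim to show treatment duration, not retention, and the protocol plans descriptive statistics only. Much of this stands, but it does not settle the clock start, the allocation rule or the missing time-at-risk limit on the numerator. Nor does it stop a raw duration from being read as persistence on drug. Kaplan-Meier estimation is itself descriptive.

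Three stronger readings are tempting and are not supported:
- A reader might infer that the non-completers' total can never be split by year. Step 1 shows that it can, given a baseline start.
- A reader might infer that a post-dose AE enters table 3.5 without any exposure. The table is cumulative on both sides, so the patient's earlier time stays in the denominator; only the post-dose time is absent.
- A reader might call it an error that a completer last seen before month 60 falls in the 54-to-60-month category. That category correctly describes the time observed. The limitation is that the table does not separate such patients from those who stopped.

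It is also fair that dropping post-dose AEs from a main rate could hide late serious events that the protocol sets out to collect. The fix allows for this.

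**Conclusion.** The point holds as a definition gap with a real, probably modest, effect on the AE rates, and as a missing censored analysis of treatment duration. The SAP does not link the table 3.5 denominator to a derived variable, does not start its clock and does not match the numerator to it.

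The net size and direction of bias in table 3.5 are unknown. Post-dose AEs alone push the rate up by about 0.6 to 6% under the assumptions in step 3, and possibly by less. Pre-baseline time in the on-drug total would push it down. For duration the direction is clear if losses occur on drug: raw summaries understate time to discontinuation. The amount depends on a loss rate that the documents do not give, and the 8 to 31 points are illustrative only. The matter should be settled in the SAP, but it does not invalidate the planned tables.

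**What to change.** **(a) Exposure for table 3.5.** Start at the baseline visit and exclude earlier drug time. End at the earliest of treatment end, the last non-LT visit and day 1826.25. Take treatment end as the last administration date if recorded, otherwise the on-drug total if it can be anchored at baseline, otherwise the last non-LT visit. Split at the existing AE year limits and apply the same dates to decide who is treated in each year of table 3.2. Label the exposure as including interruptions. Report two rates with equal prominence: one with AEs and exposure limited to this time, and one with the 3-month post-dose window added to both numerator and denominator, so that late serious events stay visible. State how many patients use each fallback and how many AE onsets are imputed, because an imputed onset may fall outside exposure.

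**(b) Treatment duration.** Keep the raw tables. Add Kaplan-Meier time to permanent discontinuation, using the reason on the Early Termination DRF and censoring patients still on drug or lost at their last real visit. State the assumption that loss is unrelated to stopping. For table 2.1.4 start the clock at the Month 6 visit, since everyone in it has been followed to at least day 138, the start of that window.

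**Cost.** SAP wording, one derivation and some extra output; no planned table is removed. Some last-dose dates may be missing. On the step 3 inputs, if 10 to 40% of stoppers fell back on a last visit 3 months after the last dose, the first rate would be 0 to 1.8% too low. The second rate, (D̄ + kT)/(D̄ + T), would be 0 to 4.4% too low if post-dose AEs are under-recorded. Showing both rates makes these limits visible.
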